- e. Health related quality of life parameters will be reported by subjects using the EORTC QLQ-C15-PAL and EQ-5D-5L questionnaires
- f. All pain -and anticancer medications (including corticoid therapy) and bone-modifying agents used during the study will be recorded. The dates of administration, method of administration, dosage, and reason for use will be included.
- g. A month can be 28, 29, 30 or 31 days, depending on the month.
- h. Occurrence of an SSE during the study should be reported to the study team immediately. In case an SSE occurs, the assessments that should take place during the next follow-up visit, should be completed at that time point, preferentially within one week. These assessments must be documented in the eCRF. Furthermore, the type of SSE (e.g. symptomatic pathological fracture,...) needs to be registered. In case of fracture or compression, the location and planned treatment must also be documented. In case of RT or surgery, the location and reason must be registered. Afterwards, only survival data will be recorded on the date of the planned FU visits until 24m after the randomization date as well as possible occurrence of another SSE within 24m after the randomization date.

Clinical Trials Oncology

Ref.Nr.: P.01-S.23

Versie: 6.0

- i. During the study (from time of study randomization to date of death of any cause or last follow-up visit (24m after randomization date) or early end of participation in the study due to other reasons), hospitalizations related to the high-risk bone metastase(s) should be documented in the eCRF. More specifically, the hospital admission date and date of discharge will be recorded as well as whether the hospitalization is related to an SSE (if yes, it should be specified to which SSE).

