- j. For each SAE, it should be evaluated whether it concerns an SSE. If it concerns an SSE, the SAE should be documented as such in the eCRF and the necessary actions should be taken (see footnote h). In case hospitalization occurs, it should be evaluated whether the hospitalization is related to the high-risk metastase(s) and this information should be documented in the eCRF. Note that only (S)AE related to the bone metastatic disease or related to radiotherapy (only applicable for arm B) must be reported in the eCRF and that all SSE need to be registered in both study arms, including an SSE in a bone metastasis that was not previously included in the study (only applicable for arm B). An exception are SSE's in bone metastases that were already treated with surgery or RT before study participation.
- k. In case of discontinuation of a subject's participation without withdrawal of consent, only survival data will be collected at the remaining follow-up timepoints (i.e. 1m, 3m, 6m, 12m, 18m and 24m after randomization date) and the occurrence of an SSE will be registered in the eCRF if it occurs within 24m after the randomization date.
- l. Patients in the upfront RT arm developing new minimally symptomatic or asymptomatic high-risk bone metastases during study participation are strongly advised to further be treated with preventive RT. Details concerning the characteristics of these new high-risk metastases as well as details regarding the preventive RT must be captured in the eCRF.

Clinical Trials Oncology

Ref.Nr.: P.01-S.23

Versie: 6.0

Administrative structure

Study responsible physician:	[name] Iridium Netwerk Department of Radiation Oncology [name]
Project managers:	Clinical Trials Office (CTO), Oncologisch Centrum ZAS [contact], [contact] [contact] www.clinicaltrials oncology.be
Sponsor	ZAS vzw, [name] [contact] www.zas.be

1. Background & Rationale

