2. Study objectives and endpoints

The primary and secondary objectives and endpoints of the study are presented in Table 2.

Table 2: Objectives and endpoints for the Hermes trial

Objectives	Endpoints
Primary	
To assess whether early preventive radiation of the high-risk asymptomatic or minimally symptomatic bone metastases in patients with metastatic cancer can decrease the number of SSEs*.	
 Time to a symptomatic skeletal related event (SSE) in any bone metastasis or death due to any cause.
Secondary	

 To evaluate the need for hospitalization related to the high-risk bone metastase(s) To assess overall survival (OS) To evaluate quality of life (QoL) 	
 The number of hospitalizations related to the high-risk bone metastases will be compared between systemic therapy/observation (arm A) and upfront RT (arm B) from date of study randomization to last follow-up visit (24m after randomization date), date of death of any cause or early end of participation in the study due to other reasons Overall survival will be assessed from time of study randomization to date of death of any cause or last follow-up visit (24m after randomization date) Quality of life will be compared between systemic therapy/observation (arm A) and upfront RT (arm B),

 To evaluate acute and late toxicity 	
using the EORTC QLQ-C15-PAL questionnaire (see appendix 2) and the EuroQol Group EQ-5D-5L questionnaire (see appendix 3)
 
 Adverse events in both study arms will be evaluated using the National Cancer Institute Common Terminology Criteria for Adverse Events (NCI-CTCAE) v5.0 (see appendix 4) from the time of ICF signing to last follow-up visit (24m after randomization date), date of death of any cause or early end of participation in the study due to other reasons. Only adverse events that are related to the bone metastatic disease or related to the radiotherapy (only for patients in arm B) will be reported in the eCRF.
---	--

*SSEs are defined as:

- symptomatic pathological fracture
- spinal cord compression leading to neurological deficit or pain
- Indication for palliative radiotherapy (for bone pain, cord compression or (impending) fracture)
- Indication for orthopedic surgery (for bone pain, cord compression or (impending) fracture)

3. Overall study design.

[figure not shown]

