7.2 Efficacy Evaluations

- Comparison of the number of SSE's in both study arms. SSEs are defined as:
 - symptomatic pathological fracture
 - spinal cord compression leading to neurological deficit or pain
 - Indication for palliative radiotherapy (for bone pain, cord compression or (impending) fracture)
 - Indication for orthopedic surgery (for bone pain, cord compression or (impending) fracture)

All SSE's will be recorded in both study arms. Patients in the upfront RT arm may develop an SSE in a bone metastasis that was not previously included in the study, which also needs to be registered. An exception are SSE's in bone metastases that were already treated with surgery or RT before study participation

Patients in the upfront RT arm developing new minimally symptomatic or asymptomatic high-risk bone metastases during study participation are strongly advised to further be treated with preventive RT. Details concerning the characteristics of these new high-risk metastases as well as details regarding the preventive RT must be captured in the eCRF.

- Comparison of the number of **hospitalizations** related to the high-risk bone metastasis(es) between observation/systemic therapy and upfront RT plus observation/systemic therapy
- **Overall survival:** from time of study randomization to date of death of any cause or last follow-up visit (24m after randomization date)
- To compare **quality of life** between observational arm (arm A) and upfront RT arm (arm B), using the EORTC QLQ-C15-PAL form and the EuroQol Group EQ-5D-5L form

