8.2 Reporting procedures

8.2.1 Method of detecting (S)AE

AE will be reported by the subject. Care will be taken not to introduce bias when detecting AE and/or SAE. Open-ended and non-leading verbal questioning of the subject is the preferred method to inquire about AE occurrences. For each SAE, it should be evaluated whether it concerns an SSE. If it concerns an SSE, the SAE should be documented as such in the eCRF and the necessary actions should be taken (see section 6.2). In case hospitalization occurs, it should be evaluated whether the hospitalization is related to the high-risk bone metastasis(es) and this information should be documented in the eCRF.

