9.3 Statistical methods for analysing primary and secondary outcomes

Primary objective:

The primary endpoint (SSE-free survival) is a composite endpoint of SSEs and death (death before SSE is part of the endpoint, not a competing risk). The primary endpoint is time until the occurrence of SSE in any bone metastasis or death from the date of randomization whichever occurs first. Data suggest that the median SSE-free survival is around 10.4 months. With a HR of 0.5, we hypothesize that the median SSE-free survival will be 20.8 months.

A proportion of patients will have multiple high-risk bone lesions. Pain will be reported lesion-based, however the SSE-free survival remains patient-based as this is more clinically relevant.

Secondary objectives

- The number of **hospitalizations** related to the high-risk metastase(s) will be compared between systemic therapy / observation (arm A) and upfront RT plus systemic therapy / observation (arm B) from date of study randomization to last follow-up visit (24m after randomization date), date of death of any cause or early end of participation in the study due to other reasons
- **Overall survival** will be assessed from time of study randomization to date of death of any cause or last follow-up visit (24m after randomization date)
- **Quality of life** will be compared between systemic therapy / observation (arm A) and upfront RT plus systemic therapy / observation (arm B), using the EORTC QLQ-C15-PAL questionnaire (see appendix 2) and the EuroQol Group EQ-5D-5L questionnaire (see appendix 3)
- **Adverse events** in both study arms will be evaluated using the National Cancer Institute Common Terminology Criteria for Adverse Events (NCI-CTCAE) v5.0 (see appendix 4) from the time of ICF signing to last follow-up visit (24m after randomization date), date of death of any cause or early end of participation in the study due to other reasons. Only adverse events that are related to the bone metastatic disease or related to the radiotherapy (only for patients in arm B) will be reported in the eCRF.

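### The hospitalisation endpoint leaves out admissions caused by radiotherapy, so it does not measure the net effect of upfront RT on the need for hospitalisation

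*Protocol*

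**What the plan says.** - **Endpoint.** Protocol section 2, Table 2: "The number of hospitalizations related to the high-risk bone metastases will be compared between systemic therapy/observation (arm A) and upfront RT (arm B". The window runs from randomisation to 24 months, death or earlier end of participation. The paired objective is "To evaluate the need for hospitalization related to the high-risk bone metastase(s". The synopsis states the aim as the need for hospitalisation and uses the same restricted count to measure it. Sections 3.1, 7.2 and 9.3 repeat the restriction.
- **Collection.** Table 1, footnote i: "hospitalizations related to the high-risk bone metastase(s) should be documented in the eCRF". Admission and discharge dates are recorded, and "whether the hospitalization is related to an SSE (if yes, it should be specified to which SSE".
- **Attribution.** Footnote j: "it should be evaluated whether the hospitalization is related to the high-risk metastase(s) and this information should be documented in the eCRF". Section 8.2.1 has the same step: "it should be evaluated whether the hospitalization is related to the high-risk bone metastasis(es". Neither place gives a rule, and section 5.2 says the trial cannot be blinded.
- **Causality of adverse events.** Section 8.1.4 asks for one of three labels: RT (arm B only), bone metastatic disease, or unrelated. Section 8.2.2 likewise limits RT-related events to arm B.
- **Primary endpoint.** Section 9.3: "The primary endpoint is time until the occurrence of SSE in any bone metastasis or death".
- **New high-risk lesions.** For the upfront RT arm, section 7.2 adds: "Details concerning the characteristics of these new high-risk metastases as well as details regarding the preventive RT must be captured in the eCRF". Arm A has no counterpart.
- **After a first SSE.** Section 6.2 and footnote h reduce recording to survival and further SSEs, whereas footnote i keeps collecting admissions to 24 months.

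**The concern.** The background section cites fewer hospitalisations in the earlier phase II trial and hopes for lower costs. A lower count in arm B would therefore be read as showing that upfront RT reduces the need for hospital care. That reading needs a net count: admissions avoided by treating the lesions, less admissions brought on by treating them. As worded, the endpoint holds the first kind and not the second. A later analysis plan could not fully repair this, because the endpoint and the instruction on which admissions to enter as hospitalisations are both fixed in the protocol.

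**Working it through.** **1. The plan's own figure.** There is none for this endpoint: no admission rate, effect size or power. The 65 events in section 9.1 belong to the primary endpoint and have no bearing here.

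**2. Which admissions are counted.** Sections 2, 5.1, 6.2, 7.2, 8.1.2, 8.1.4 and 8.2.2 and the Table 1 footnotes, set side by side, give:

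| Reason for admission | In the count? | Recorded elsewhere? |
|---|---|---|
| Enrolled high-risk lesion, either arm | Yes | SAE related to bone disease |
| SSE in another bone lesion, either arm | No | SSE, and SAE related to bone disease |
| New high-risk lesion | Not stated | Lesion details required in arm B only |
| Toxicity of RT, arm B | No, on the plain wording | SAE related to RT |
| Toxicity of palliative RT, arm A | No, on the plain wording | The RT-related label is not open to arm A |
| High-risk lesion, after a first SSE | Yes by footnote i; not by section 6.2 and footnote h | Conflict to reconcile |

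**3. Which arm loses more RT admissions.** Every arm B patient is planned to be irradiated, at up to 5 sites, with SABR for NRF score 0-1. In arm A, RT is given only on an SSE. Section 9.1 assumes 20% of arm A free of SSE and death at 2 years, so at most 100% - 20% = 80% of arm A would have had an SSE, and fewer if deaths come first. This sets aside re-treatment of lesions treated before entry, whose SSEs are not counted. Arm B patients can also receive palliative RT later. More RT admissions in arm B are therefore likely, but this is not certain, and the documents give no rate for either arm.

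**4. Illustration on assumed rates only.** Let a and b be admissions per patient over 24 months for high-risk lesions in arms A and B, and rA and rB the RT-caused admissions. The present ratio is b/a. With RT admissions included it is (b + rB)/(a + rA).

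- Take a = 0.30, b = 0.15: present ratio 0.15/0.30 = 0.50.
- With rA = 0 and rB = 0.02, 0.05, 0.10 (1.2, 3 and 6 admissions in 60 patients): 0.17/0.30 = 0.57, 0.20/0.30 = 0.67, 0.25/0.30 = 0.83.
- With rA = 0.02 and rB = 0.05: 0.20/0.32 = 0.625. The difference falls from 0.15 to 0.32 - 0.20 = 0.12.
- With rA = rB = 0.05: 0.20/0.35 = 0.57, and the difference stays at 0.15.
- With a weaker effect, a = 0.30, b = 0.24 (ratio 0.80), rA = 0 and the same rB values: 0.26/0.30 = 0.87, 0.29/0.30 = 0.97, 0.34/0.30 = 1.13.

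**5. Other bone lesions.** Let u be admissions per patient for other lesions, equal in both arms, with no RT admissions. With u = 0.1 the ratio is 0.25/0.40 = 0.625; with u = 0.2 it is 0.35/0.50 = 0.70. The difference is 0.15 in each case. Leaving these admissions out makes the ratio look stronger and does not change the absolute difference.

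**The case against.** The endpoint matches its Table 2 objective, and the restriction is worded consistently throughout. A cause-specific secondary endpoint aimed at the treated lesions is legitimate and need not share the scope of the primary endpoint. RT harm is not lost: a hospitalisation makes an event serious, and RT-related serious events in arm B are reported under toxicity. Section 10.1.4 expects no high-grade side effects. The exclusion is also inferred, because no sentence says that an admission after irradiating a high-risk lesion is unrelated to that lesion.

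Much of this stands. There is no internal contradiction, and the effect may be small. But the statement on side effects follows a sentence about conventional radiotherapy, and SABR is also planned. Reporting RT admissions under toxicity does not put them into the comparison. If sites may code an RT-caused admission either way, the same event can be counted at one site and not at another, with staff aware of the arm.

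A reader might infer that the endpoint favours RT by construction. The documents do not support that:

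- Admissions for other bone lesions are left out in both arms.
- Missing records for new high-risk lesions in arm A would, if anything, lower arm A's count and work against RT.
- Arm A patients receive palliative RT, and admissions for its toxicity are left out too.
- If section 6.2 is followed, admissions after a first SSE are lost more often in the arm with more SSEs, which the design expects to be arm A.

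**Conclusion.** The point holds as a weakness of scope. On its plain wording the endpoint counts admissions that upfront RT may prevent and omits those that RT may cause, so it does not measure the net effect on the need for hospitalisation. The omission favours arm B to the extent that RT-caused admissions are more frequent there, which is likely but not shown. Its size cannot be estimated from the documents; the ratios above rest on assumed rates and show only how sensitive the result is. The narrower scope compared with the primary endpoint strengthens a ratio but is not in itself a bias towards RT. The conclusion assumes that sites read relatedness to the high-risk lesions as section 8.1.4 separates RT from bone disease.

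**What to change.** In the synopsis, Table 2, section 3.1, Table 1 footnotes i and j, and sections 7.2, 8.2.1 and 9.3, compare between arms the number of hospitalisations related to any bone metastasis or to any radiotherapy to bone, whether upfront or palliative. Show the present high-risk-lesion count as a component.

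For these admissions record, in both arms, the admission and discharge dates and a reason code: high-risk lesion, other or new bone lesion, or RT. Lift the arm-B-only limit on RT-relatedness for this record. Otherwise the existing capture in sections 8.1.4 and 8.2.2 would add RT admissions to arm B alone and tilt the comparison the other way.

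Reconcile section 6.2 and footnote h with footnote i on whether admissions are still recorded after a first SSE.

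The cost is an amendment of wording, one reason code, and slightly more eCRF collection in arm A. Relatedness would still be judged unblinded, and the result may look less favourable to RT.

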3.1 General scheme of study design

The HERMES study is a phase III randomized controlled trial to investigate if early, upfront RT for asymptomatic or minimally symptomatic high-risk bone metastases can prevent symptomatic skeletal events. The primary outcome is the time to a symptomatic skeletal event (SSE) or death due to any cause. Secondary outcomes are overall survival, early and late adverse effects, quality of life and need for hospitalization related to the high-risk bone metastase(s).

The study will be conducted in various centers (inter)nationally.

Participation in the HERMES study will comprise a screening period, during which the screening assessments must be completed. Eligible, consenting subjects will then be randomized (1:1) into one of two treatment arms: an observational arm (arm A) receiving systemic therapy / observation or an upfront RT arm (arm B) receiving upfront RT plus systemic therapy / observation. RT should take place within 21 days after date of randomization for subjects in arm B. Afterwards, onsite follow-up visits will take place at 1, 3, 6, 12, 18 and 24 months after date of randomization during which safety and efficacy are monitored.

The screening, treatment and follow-up schedules are presented in Table 1. A schematic presentation of the study design is shown in Figure 1.

Abbreviations: R = Randomization

Figure 1: Schematic representation of study design of the HERMES study.

3.2 Study duration, enrolment and number of sites

3.2.1 Duration of study participation

The total study duration will be 4 years, with an accrual period of 2 years. The total follow-up period will be 2 years for each patient.

3.2.2 Total number of study sites/total number of subjects projected

The HERMES study is a multicenter randomized trial. The total sample size of the study will be 120. We aim for randomization of a total of 96 patients (48 in each treatment arm) as a drop-out of 20% is assumed. More information with regard to the statistics can be found in section 9.

4. Study population

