4.1 Definitions

Subjects officially enter the screening period following provision of informed consent either directly or via a legally authorized representative (LAR). Screening for eligible subjects will be performed within 3 weeks before randomization.

Eligible, consenting subjects will be enrolled to the study. Prior to enrollment of a subject, the following must occur:

- Confirmation that the subject has signed the informed consent form (ICF).
- Confirmation that the subject meets all of the inclusion and none of the exclusion criteria.

The inclusion and exclusion criteria for enrolling subjects in this study are described in the following sections. Enrollment will occur only if the subject meets all study eligibility criteria and has been assessed by the Investigator as being an appropriate candidate for study participation. If there is a question about any of these criteria, the investigator must consult with the appropriate Sponsor representative and resolve any issues before enrolling a participant in the study. If a participant's clinical status changes (including any available laboratory results or receipt of additional medical records) after screening but before treatment such that he or she no longer meets all eligibility criteria, then the subject should be excluded from participation in the study.

An enrolled subject is one who has been deemed eligible and has been assigned to a treatment group.

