9.1 Justification of sample size

In collaboration with statistical experts UGent a sample size calculation was performed. A hazard ratio of 0.5 is deemed clinically relevant, increasing the estimated 2-year SSE free survival from 20% to 45%. Assuming exponentially distributed SSE-free survival, setting alpha to 0.05 and the required power to 0.8 and assumed non-informative drop out to 20%, this results in a sample size of 120 (96 without drop out) with a required number of events of 65.

Hazard ratio (HR) = 0.5 is in between previously observed effect sizes in similar settings: Different trials analyzing the use of bone modifying agents with the presence of SREs, showing a HR around 0.7 [Smith et al; O’Carrigan et al; Rosen et al]]. In the above-mentioned phase II trial [Rosen et al] there was a large reduction in SREs from incidence from 29% to 1.6% at 1 year in the RT group. Because in our trial SSEs and not SREs will be analyzed, we expect a more conservative HR. This was also demonstrated in a trial comparing skeletal-related events with symptomatic skeletal events for two different bone modifying agents [Smith et al].

A sample size of 96 patients was calculated to have an 80% power and an $\alpha < 0.05$. With an estimated dropout of 20%, the **total sample size will be 120** with a required number of events of 65.

Each patient will be stratified by their prognostic class (0-1 vs 2), high-risk disease location (spine location vs. other) and bone modifying agents (yes vs. no) in this hierarchical order. With 3 stratification factors for randomization, there are 8 strata, which is rather high for only 60 patients per arm. Strata where only 1 arm is present and the events in these strata, are implicitly ignored in the estimation/testing. Strata with less than 10 patients will be merged with the corresponding stratum with the same value for factor A and B, but different value for C in the upfront decided hierarchical order (cfr above).

Randomization will be completed on a per patient basis (not lesion based), even though each patient may have up to 5 multiple sites of metastatic bony disease.

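### Section 3.2.2 sets the randomisation target at 96 (48 per arm), but section 9.1 needs 120 randomised (60 per arm); 96 with 20% drop-out gives about 52 to 60 events and 70% to 76% power

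*Protocol*

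**What the plan says.** Section 3.2.2 first gives a total sample size of 120, as the synopsis does. It then sets the number to be randomised: "We aim for randomization of a total of 96 patients (48 in each treatment arm) as a drop-out of 20% is assumed".

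Section 9.1 assumes exponential SSE-free survival, a hazard ratio of 0.5, 2-year SSE-free survival rising from 20% to 45%, alpha 0.05, power 0.8 and 20% non-informative drop-out. It concludes that "this results in a sample size of 120 (96 without drop out) with a required number of events of 65", and says again: "With an estimated dropout of 20%, the total sample size will be 120 with a required number of events of 65". On the randomisation strata it remarks that "there are 8 strata, which is rather high for only 60 patients per arm".

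Section 4.1 ties enrolment to allocation: "An enrolled subject is one who has been deemed eligible and has been assigned to a treatment group". Section 9.3 counts the primary endpoint from the date of randomisation.

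**The concern.** The two sections give different numbers to randomise: 48 per arm in 3.2.2 and 60 per arm in 9.1. Section 3.2.2 cites the 20% drop-out as its reason for 96, but 96 is the figure in section 9.1 that contains no allowance for drop-out.

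Non-informative drop-out in a survival calculation means censoring. It affects patients whose time is already running from randomisation, so it cannot be subtracted from the number randomised. If recruitment stops at 96, the design keeps no allowance for loss after randomisation and misses both the 65 events and the 80% power on which the primary analysis depends.

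**Working it through.** **Inputs.** Hazard ratio 0.5, alpha 0.05, power 0.8, drop-out 20% (section 9.1); medians 10.4 and 20.8 months (section 9.3); 24 months of follow-up per patient (section 3.2.1); 1:1 allocation (section 3.1). The protocol gives neither the sidedness of alpha nor the timing of drop-out. Two-sided alpha is assumed because it reproduces the plan's event count; one-sided alpha gives 52 events by the same formula.

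**Step 1: reproduce section 9.1.**
- Required events (Schoenfeld, 1:1): 4 × (1.960 + 0.842)² / (ln 0.5)² = 65.3, against 65 stated.
- Event probability at 24 months: arm A 1 − 2^(−24/10.4) = 0.798; arm B 1 − 2^(−24/20.8) = 0.551; mean 0.674.
- Patients needed with complete follow-up: 65/0.674 ≈ 96.
- Allowing for 20% drop-out: 96/0.8 = 120, or 60 per arm.

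All three figures in section 9.1 are reproduced. They show that 96 assumes no loss and that 120 is the number to randomise.

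**Step 2: randomise 96 or 120 and apply the 20% drop-out.** Power = Φ(√events × |ln 0.5|/2 − 1.96).

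- *No drop-out:* 96 × 0.674 = 64.7 events, power 79.6%.
- *Drop-outs contribute nothing* (the logic of 96/0.8): 96 × 0.8 × 0.674 = 51.8 events. Power = Φ(7.20 × 0.3466 − 1.96) = Φ(0.53) = 70.3%.
- *Constant drop-out hazard reaching 20% at month 24:* hazard μ = −ln(0.8)/24 = 0.0093 per month. The probability of an observed event is λ/(λ+μ) × [1 − exp(−(λ+μ) × 24)] with λ = ln 2/median. This gives 0.736 (A) and 0.501 (B), mean 0.618. Events 96 × 0.618 ≈ 59.4, power 76.1%.

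Two further patterns were computed from the 20% two-year survival figure with hazard ratio 0.5, a basis that differs only in rounding.

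| Drop-out pattern | 96 randomised: events, power | 120 randomised: events, power |
|---|---|---|
| Drop-outs contribute nothing | 51.8, 70.3% | 64.7, 79.6% |
| 20% of patients seen to drop out before an event | 55.9, 73.6% | 69.8, 82.5% |
| Constant hazard, 20% by month 24 | 59.4, 76.1% | 74.2, 84.7% |
| 20% leave evenly over 24 months | 59.8, 76.4% | 74.7, 85.0% |

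At 96 every pattern falls short of 65 events and 80% power. At 120 the strictest pattern gives 65 events to rounding, and the others exceed it.

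**The case against.** The strongest defence is that this is one misworded sentence in a protocol that otherwise says 120: in the sentence just before it, in the synopsis and in section 9.1. That is fair as to intent, and the sample-size calculation itself is sound. But this sentence is the only one that states how many patients to randomise.

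A second defence reads 120 as consented and 96 as randomised, pointing to section 4.5, where consented patients who do not start treatment are screen failures. This fails. Section 9.1 speaks of "which is rather high for only 60 patients per arm", and patients belong to an arm only once randomised. The drop-out in section 9.1 is a censoring assumption, whereas losses before allocation have their own name in section 4.5. This reading would also leave nothing for loss after randomisation.

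Third, 70% power is a lower bound. Section 6.3.1 keeps data up to withdrawal of consent and continues to register SSEs and survival in patients who discontinue without withdrawing consent. This stands: about 76% is nearer to what those rules imply, and the loss could be smaller still if many who stop remain under follow-up. However, 96 reaches about 65 events only with no loss at all.

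Finally, the blinded review in section 9.4 may add patients or extend follow-up. That makes an unnoticed shortfall less likely, but any such action depends on its result, and it does not settle the planned number. No passage says that the randomisation tool is capped at 96, so the harm arises only if section 3.2.2 is followed as written.

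**Conclusion.** The contradiction is real and must be corrected. Section 3.2.2 presents as the randomisation target a number that section 9.1 derives for a trial without drop-out. Followed literally, it yields about 52 to 60 events instead of 65, and 70% to 76% power instead of 80%. The range reflects the unstated timing of drop-out. The result assumes two-sided alpha, exponential survival with the protocol's medians, and 24 months of follow-up per patient. Randomising 120 gives about 65 to 75 events and 80% to 85% power under the same assumptions.

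**What to change.** Replace the sentence on randomisation in section 3.2.2 with, for example: *A total of 120 patients (60 per arm) will be randomized. This allows for 20% drop-out relative to the 96 patients who would be needed with complete follow-up to observe 65 events (section 9.1).* This wording avoids suggesting a separate analysis set of 96, since section 9.2 analyses patients by randomised assignment. If the electronic randomisation tool described in section 5.2 holds a recruitment limit, check that it is set to 120.

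The cost is one sentence in the next amendment. The total of 120 is already stated in the synopsis and section 9.1, so no design parameter changes and no patients are added.
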